### NUMBER OF SUBJECTS

The total number of subjects to be randomised is approximately 300, i.e. 200 randomised to treatment with REKOVELLE and 100 randomised to treatment with GONAL-F.

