### 1 INTRODUCTION

### 1.1 Background

Follitropin delta (REKOVELLE) is a novel human recombinant follicle-stimulating hormone (rFSH) derived from a human cell line (PER.C6®). It is intended for the development of multiple follicles during controlled ovarian stimulation (COS) in women undergoing assisted reproductive technologies (ART) such as an in vitro fertilisation (IVF) or intracytoplasmic sperm injection (ICSI) cycle. The first Marketing Authorisation approval was obtained by the European Commission in December 2016, and as of 01 May 2021 REKOVELLE is approved in 69 countries and regions worldwide.

The currently approved REKOVELLE dosing regimen is based on each woman's serum anti-Müllerian hormone (AMH) concentration and her body weight, and is a fixed-dose regimen with the daily dose maintained throughout the stimulation period. The approved maximum daily dose of REKOVELLE is 12  $\mu$ g for the first treatment cycle and 24  $\mu$ g in subsequent treatment cycles. Other approved rFSH preparations, such as follitropin alfa (GONAL-F) and follitropin beta (PUREGON / FOLLISTIM), apply a conventional dosing approach with a starting dose of 150-225 IU, fixed for the initial days of stimulation, followed by the possibility for subsequent dose adjustments, with a maximum daily dose of 450 IU.

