#### **3.2** Determination of Sample Size

In a previous trial (MERIT), 347 subjects aged 22-37 years were treated with a starting dose of 225 IU GONAL-F. In these subjects the mean number of oocytes retrieved was 11.8 and the standard deviation was 5.7. Assuming that the standard deviation for number of oocytes retrieved in this trial will be 6.0, a total sample size of 300 with a 2:1 randomisation will give a 2-sided 95% confidence interval ranging from -1.44 to +1.44 oocytes from the observed difference. This level of precision is considered as sufficient and is also more precise than the equivalence limits of  $\pm 3$  oocytes that has been applied in previous trials comparing biosimilar FSH compounds.

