## 7.1.2 Body Measurements

The following body measurements at screening will be summarised: Body weight (kg), body weight category (<45, 45-<55, 55-<65, 65-<75, 75-<85, 85-<95,  $\geq95$ ), height (m), BMI (kg/m^2), BMI category (<18.5, 18.5-<25.0, 25.0-<30.0,  $\geq30.0$ ).

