#### 7.1.4 Transvaginal ultrasound

The number of antral follicles on stimulation day 1 will be summarised and tabulated using categories (0-4, 5-9 and  $\geq$ 10 antral follicles).

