#### **10.1 Primary Efficacy Endpoint**

The primary endpoint, number of oocytes retrieved, will be compared between REKOVELLE and GONAL-F using a negative binomial regression model with treatment and AMH level at stimulation day 1 (AMH <15 pmol/L, AMH  $\geq$ 15 pmol/L, or missing) as factors. The absolute treatment difference in number of oocytes retrieved, the associated 95% confidence interval, and the p-value for no treatment difference will be derived from the model estimates using the delta method.

The distribution of the number of oocytes retrieved will be visualised in histograms. Furthermore, the number of oocytes will be grouped and presented in tables and figures using the following classification:

- <4 oocytes or cycle cancellation due to poor ovarian response
- 4-7 oocytes
- 8-14 oocytes
- 15-19 oocytes
- $\geq 20$  oocytes or cycle cancellation due to excessive ovarian response
- Cycle cancellation due to another reason than poor or excessive ovarian response

The treatment difference will also be investigated for sub-groups defined by AMH level at stimulation day 1 (i.e. <15 pmol/L, AMH  $\geq$ 15 pmol/L or missing) using the same methods as above for each sub-group separately.

No formal hypothesis testing will be conducted using these methods.

As a supplementary analysis, the analysis of the primary endpoint will be repeated using the PP analysis set and corresponding summary tables will be presented.

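### The primary model adjusts only for AMH category; antral follicle count and body weight, both recorded before treatment, could narrow the interval by an amount the documents do not let us derive.

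*Combined protocol and SAP*

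**What the plan says.** Protocol 9.7.2 and SAP 10.1 specify the same primary analysis, a "negative binomial regression model with treatment and AMH level at stimulation day 1" (below 15 pmol/L, 15 pmol/L or above, or missing). Nothing else enters. SAP section 10 bases the results on least-squares means at the observed margins. SAP 10.1 obtains the absolute difference and its interval by the delta method and repeats the analysis separately within each AMH group, including the missing group.

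Two other baseline measurements are used only descriptively:

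- **Follicle count.** Protocol 6.2.1 schedules an ovarian ultrasound with number and size of follicles before the first dose, and footnote c of SAP Table 3-1 confirms the timing. SAP 7.1.4 states: "The number of antral follicles on stimulation day 1 will be summarised".
- **Body weight.** It is measured at screening (protocol 7.4.4), and SAP 7.1.2 lists "Body weight (kg), body weight category" among the summaries.

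Protocol 1.1 describes the approved REKOVELLE regimen as depending on the woman's anti-Müllerian "hormone (AMH) concentration and her body weight, and is a fixed-dose regimen". In this trial all REKOVELLE subjects start on one dose and all GONAL-F subjects on another, with later changes guided by response.

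On precision, SAP 3.2 promises a "2-sided 95% confidence interval ranging from -1.44 to +1.44 oocytes from the observed difference" and calls that sufficient.

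**The concern.** The trial is designed for estimation. It sets no margin or power of its own, and the sample size is justified only by the width of one interval. A baseline variable that predicts the outcome can narrow that interval in a randomised comparison and can absorb chance imbalance. Randomisation is stratified by site only (protocol 4.2.2), so imbalance in follicle count or weight in a 200 to 100 split is handled neither by the design nor by the model.

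Both variables are credible candidates on the documents' own content. The drug is given to make multiple follicles develop, and oocytes are collected from follicles, so the number present at baseline should bear on yield. Weight helps set the approved REKOVELLE dose but does not set the starting dose here, so any influence it has on response may remain in the outcome. The plan adjusts for AMH and leaves out the other variable named with it.

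The AMH subgroup analyses have the least adjustment. Within one AMH group the AMH factor is constant, so the planned model reduces to treatment alone.

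**Working it through.** **Inputs**

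- Standard deviation: "Assuming that the standard deviation for number of oocytes retrieved in this trial will be 6.0" (SAP 3.2).
- Group sizes: "200 randomised to treatment with REKOVELLE and 100 randomised to treatment with GONAL-F" (protocol synopsis).
- For the previous trial, "the mean number of oocytes retrieved was 11.8 and the standard deviation was 5.7" (SAP 3.2). The mean of 11.8 is used only to set up the simulation in step 4.
- Share *r* of the variance left after AMH category that follicle count and weight would explain: not given in the documents. Assumed values are 0, 5%, 10% and 20%.

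**Step 1. The plan's own figure.** Half-width = 1.96 × 6.0 × √(1/200 + 1/100) = 1.96 × 6.0 × 0.1225 = 1.44. It reproduces, and no covariate is involved.

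**Step 2. Relative gain.** Adding the covariates multiplies the half-width of the AMH-adjusted interval by √(1 − *r*). The equivalent sample size is 300/(1 − *r*).

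| *r* (assumed) | √(1 − *r*) | Narrower by | Equivalent to extra subjects |
|---|---|---|---|
| 5% | 0.975 | 2.5% | 16 |
| 10% | 0.949 | 5.1% | 33 |
| 20% | 0.894 | 10.6% | 75 |

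These percentages apply to the interval after AMH adjustment, whose width the documents do not state. They must not be applied to 1.44, which is the width with no adjustment.

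**Step 3. Cost if *r* = 0.** In a linear-model approximation with t quantiles, two extra parameters multiply the residual standard deviation by √(298/296) = 1.003. The half-width moves from 1.446 to 1.451, an increase of under 0.5%.

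**Step 4. Check in the planned type of model.** For each setting, 400 negative binomial trials were simulated with mean 11.8 and SD about 6. AMH group was assumed to explain 15% of total variance, and one further covariate was added. LS means are taken at the observed margins; averaged means are predictions averaged over all subjects.

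| Added share of total variance (assumed) | Half-width, AMH only, LS means | Half-width, adjusted, LS means | Half-width, adjusted, averaged | Control mean, adjusted, LS means | Control mean, adjusted, averaged |
|---|---|---|---|---|---|
| 0 | 1.287 | 1.287 | 1.312 | 11.54 | 11.77 |
| 5% | 1.286 | 1.239 | 1.271 | 11.51 | 11.82 |
| 10% | 1.277 | 1.186 | 1.225 | 11.42 | 11.80 |
| 20% | 1.286 | 1.096 | 1.146 | 11.30 | 11.82 |

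Two things follow.

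- With averaged predictions, the 20% row is 1 − 1.146/1.312 = 12.7% narrower than the 0 row. The formula agrees: 20% of the total is 0.20/0.85 = 23.5% of what AMH leaves, and 1 − √(1 − 0.235) = 12.5%.
- With least-squares means the same row appears 1 − 1.096/1.287 = 14.8% narrower. The excess is rescaling. Under a log link the back-transformed control mean falls to 11.30, against 11.82 when averaged. That ratio, 0.956, is also the ratio of the half-widths (1.096/1.146). A stronger covariate therefore shrinks the absolute difference together with its interval.

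**The case against.** The sponsor can fairly reply that nothing is broken. Protocol and SAP agree on the model, the analyses are declared descriptive, randomisation protects validity, and the stated precision is reached without any covariate. As an illustration only, since the trial adopts no margin, under true equality the unadjusted interval already falls within the ±3 oocytes quoted from earlier trials with probability 96.6%. All of this stands, and it is why the point is one of efficiency.

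The sponsor can also say that the premise is thin, and this stands too. Neither document gives a correlation of follicle count or weight with oocytes, or says that follicle count is prognostic. AMH category may already carry part of the follicle signal. AMH is measured centrally, whereas follicles are counted at 15–20 sites with no counting standard in these documents. The weight statement concerns the approved individualised regimen. It makes weight a plausible predictor here but does not show its strength, or that one slope fits both arms; and response-guided dose changes may absorb some of its effect.

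A reader might infer that the plan loses a known amount of precision, or that ±1.44 would become 1.40, 1.37 or 1.29. The documents support neither. The share explained is assumed, and 1.44 does not include the AMH adjustment from which that share is counted.

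Two practical objections change the remedy. Continuous covariates combined with least-squares means shift the absolute estimate (step 4), and the missing-AMH subgroup may be too small for two extra slopes.

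**Conclusion.** The omission is confirmed: two pre-treatment variables, already collected and plausibly related to oocyte yield at a common starting dose, are left out of the primary model. The consequence is a possible efficiency gain and nothing stronger. On assumed shares of 5%, 10% and 20% of the variance left after AMH category, the interval would be about 2.5%, 5% and 11% narrower than the AMH-adjusted one. With a share of zero it would be under 0.5% wider. The true share cannot be derived from the documents.

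The point does not show bias, an invalid interval or a shortfall against the planned precision, and should not be read that way. Low priority, but cheap to act on.

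**What to change.** Before unblinding, amend SAP 10.1 as follows:

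1. Add log(antral follicle count + 1) and log(body weight) as pre-specified covariates in the primary model and in the related count models of SAP 10.2 (follicles, fertilised oocytes, blastocysts). Substitute the mean for a missing covariate value.
2. Obtain the absolute difference and its delta-method interval from predictions averaged over all subjects, in place of least-squares means at the covariate means.
3. Keep the AMH-only model as a supportive analysis. Computing it from averaged predictions as well would keep the two results on the same scale.
4. Report the missing-AMH subgroup descriptively, or without the extra covariates, if it is too small to support them.

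The cost is a few sentences, an entry in SAP section 13, two more parameters per model, and a primary estimate that may differ slightly from the AMH-only one. No new data are needed.

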#### **10.2** Secondary Efficacy Analyses

In addition to summary tables, some secondary endpoints will be compared between REKOVELLE and GONAL-F using statistical models. An overview is shown in Table 10-1 and further details on the statistical models are provided below.

 Table 10-1
 Overview of analysis methods for secondary endpoints

	Analysis method				
Secondary Endpoints	Summary tables	Negative binomial regression	ANCOVA	ANOVA	
Number of follicles in total and by size category at EOS	Х	Х			
Serum concentration of estradiol at EOS	Х		Х		
Serum concentration of progesterone at EOS	Х		Х		
Number of fertilised oocytes (2PN)	Х	Х			
Fertilisation rate	Х	Х			
Number of blastocysts in total and by quality	Х	Х			
Gonadotropin dose in total and average daily dose	Х				
Number of dose adjustments	Х				
Number of stimulation days	Х			Х	
Incidence of early OHSS overall and by grade	Х				
Preventive interventions for early OHSS	Х				

#### Number of Follicles at End-of-stimulation

The follicle cohort at end-of-stimulation (EOS) will be summarised by treatment on the subject level (i.e. total number of follicles, and number of follicles  $\geq 10 \text{ mm}$ ,  $\geq 12 \text{ mm}$ ,  $\geq 15 \text{ mm}$  and  $\geq 17 \text{ mm}$ ). Additionally, the mean number of follicles  $\geq 10 \text{ mm}$ ,  $\geq 12 \text{ mm}$ ,  $\geq 15 \text{ mm}$  and  $\geq 17 \text{ mm}$  at EOS will (in separate analyses) be compared between treatments using the same negative binomial regression model as used for the primary endpoint.

# Serum Concentrations of Estradiol and Progesterone at End-of-stimulation

Serum concentrations of estradiol and progesterone at EOS will be compared between treatments using analysis of covariance (ANCOVA) models with treatment and AMH level at stimulation day 1 (AMH <15 pmol/L, AMH  $\geq$ 15 pmol/L, or missing) as factors and with the serum concentration (log-transformed) at stimulation day 1 as a covariate. Multiplicative models will be used, i.e. the serum concentrations will be log-transformed before analysis. The results of the analyses will be back-transformed and presented as estimated geometric means and mean treatment ratios with 95% confidence intervals and p-values. Values below the lower limit of quantification (LLOQ) will be estimated with LLOQ/2. Potential values above the upper limit of quantification (ULOQ) will be included as ULOQ.

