### 6.2.3 End-of-stimulation

The end-of-stimulation visit will take place when the subject reaches the criterion for triggering of final follicular maturation. Triggering of final follicular maturation will be done either with hCG or GnRH agonist, depending on the extent of ovarian response and whether transfer in the fresh cycle or in a subsequent frozen cycle (including a freeze-all approach) is intended. Administration of REKOVELLE or GONAL-F after reaching the triggering criterion is not allowed.

Criterion for triggering of final follicular maturation with 250 µg hCG:

• ≥3 follicles with a diameter of ≥17 mm and intended transfer in the fresh cycle [*note:* triggering can also be done in case 1 or 2 follicles with a diameter ≥17 mm are observed and the investigator judges that ≥3 follicles with a diameter ≥17 mm cannot be reached, and that triggering is preferred instead of cycle cancellation]

Additional criteria for triggering of final follicular maturation with 0.2 mg GnRH agonist:

- $\geq 25$  follicles with a diameter of  $\geq 12$  mm or
- serum estradiol concentration ≥5,000 pg/mL (18,355 pmol/L) (local laboratory) or
- intended freeze-all approach

Moreover, if these criteria for triggering with GnRH agonist are not met, but the investigator judges that the subject is at risk of developing early OHSS and that triggering with hCG is not advisable, the subject can undergo triggering with GnRH agonist.

In case of poor ovarian response, defined as the investigator judging that the triggering criterion cannot be reached by day 20, the cycle is to be cancelled. In case of excessive ovarian response, defined as the investigator judging that triggering of final follicular maturation is not advisable due to safety concerns, the cycle is to be cancelled.

The investigator also has the option of cancelling the cycle for other relevant medical reasons, including adverse events.

The following must take place at the end-of-stimulation visit:

- Transvaginal ultrasound of ovaries (number and size of follicles)
- Blood collection for central laboratory analysis of endocrine parameters (estradiol, and progesterone)
- Dispensing of hCG or GnRH agonist, as applicable
- Drug accountability of IMP and GnRH antagonist
- Recording of use of any concomitant medication
- Recording of adverse events

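### If a material share of end-of-stimulation estradiol values exceeds the central assay's ULOQ, entering them as the ULOQ biases the treatment ratio; a right-censored fit of the same model would not

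*Combined protocol and SAP*

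**What the plan says.** SAP 10.2 (Serum Concentrations of Estradiol and Progesterone at End-of-stimulation) specifies an ANCOVA with treatment and AMH level as factors and the log day-1 concentration as covariate. On scale it says: "Multiplicative models will be used, i.e. the serum concentrations will be log-transformed before analysis". Results are to be "back-transformed and presented as estimated geometric means and mean treatment ratios with 95% confidence intervals and p-values".

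Out-of-range values are handled by substitution at both ends. At the bottom: "Values below the lower limit of quantification (LLOQ) will be estimated with LLOQ/2". At the top: "Potential values above the upper limit of quantification (ULOQ) will be included as ULOQ". Protocol 9.7.3 has the same two rules, and SAP section 13 lists no change to them.

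Protocol 7.2.2 assigns these samples to a central laboratory. Neither document gives the ULOQ, a dilution or re-assay rule, the expected share above the limit, a count of such values by arm, or a sensitivity analysis for them. SAP section 10 calls all analyses descriptive, and no margin is set for either hormone.

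**The concern.** A result above the ULOQ is known only to exceed a limit, yet the ANCOVA would read it as an exact measurement at that limit. When the arms differ in level but not in spread, the higher arm has more values cut back, so the estimated difference in log means is too small. The confidence interval is then centred on a biased value.

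This matters most for estradiol. Protocol 1.2 names end-of-stimulation estradiol among the measures of the comparable ovarian response established at 150 IU, the basis for extrapolating to 15 µg and 225 IU. In a descriptive comparison the ratio and its interval are the result, and those are the quantities the rule would distort.

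**Working it through.** **Design inputs.** SAP 3.2 gives "a total sample size of 300 with a 2:1 randomisation", hence 200 and 100 subjects. It assumes the SD for "number of oocytes retrieved in this trial will be 6.0" and reports a "2-sided 95% confidence interval ranging from -1.44 to +1.44 oocytes from the observed difference". Check: 1.96 × 6.0 × √(1/200 + 1/100) = 1.440, so the plan's figure is reproduced. It concerns oocytes; there is no counterpart for the hormones.

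**Assumptions not in the documents.** Log-normal concentrations; log SD 0.6 in both arms (0.5 to 0.9 was also examined); true REKOVELLE/GONAL-F ratio 1.20; share above the ULOQ up to 30%.

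**Formula.** For Y ~ N(μ, s²) on the log scale, log-ULOQ c and a = (c − μ)/s:

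E[min(Y, c)] = μΦ(a) − sφ(a) + c(1 − Φ(a)).

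Its derivative in μ is Φ(a), the share below the ULOQ. The log ratio is therefore multiplied by about one minus the share above it.

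**Worked case, 20% above.** Put the GONAL-F log mean at 0 and the REKOVELLE log mean at ln 1.20 = 0.1823. With c = 0.632, 22.7% of REKOVELLE and 14.6% of GONAL-F values exceed the limit; (2 × 22.7 + 14.6)/3 = 20.0%. After substitution the means are 0.1035 and −0.0451. The difference is 0.1486 and the ratio exp(0.1486) = 1.160. The log ratio keeps 0.1486/0.1823 = 81.5% of its size.

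**Coverage in that case.** The bias is b = 0.1486 − 0.1823 = −0.0337. The pooled SD falls from 0.60 to 0.50, so the model SE is 0.50 × √0.015 = 0.0612; the true SD of the estimator is 0.0629. With t = 1.968 on 298 df:

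Φ((1.968 × 0.0612 + 0.0337)/0.0629) − Φ((−1.968 × 0.0612 + 0.0337)/0.0629) = Φ(2.45) − Φ(−1.38) = 0.91.

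Setting b = 0 gives Φ(1.915) − Φ(−1.915) = 0.945, so nearly all the lost coverage comes from bias.

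| Share above ULOQ | Log ratio lost | Estimated ratio (true 1.20) | 95% CI coverage |
|---|---|---|---|
| 2% | 1.7% | 1.196 | about 95% |
| 5% | 4.4% | 1.190 | about 95% |
| 10% | 9.0% | 1.180 | about 94% |
| 20% | 18.5% | 1.160 | about 91% |
| 30% | 28.2% | 1.140 | about 84% |

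For 5% and above, 40,000 simulated two-group comparisons gave coverage of 94.8, 93.9, 90.8 and 83.5%.

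**Under the planned model.** A simulated ANCOVA with treatment, AMH class and log baseline (n = 300, log SD 0.7, true ratio 1.20) lost 0.9, 4.5, 9.0 and 19.0% of the log ratio at 1, 5, 10 and 20% above the ULOQ.

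**Unequal spread.** With log SD 0.6 for REKOVELLE and 0.8 for GONAL-F, a true ratio of 1.00 becomes 1.023 at 5% and 1.039 at 10%, away from 1. With the SDs swapped it becomes 0.982 and 0.968. With equal SDs a true ratio of 1 stays at 1.

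**Alternative.** In 400 simulated trials per scenario (log SD 0.7, true ratio 1.20), at 5, 10 and 20% above the ULOQ:

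- complete data: 1.196, 1.191, 1.200;
- right-censored fit: 1.196, 1.191, 1.200;
- ULOQ substitution: 1.188, 1.172, 1.161.

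**The case against.** The strongest reply is that the problem may never arise. The rule speaks of potential values, which makes it a contingency. A reader might infer that high values are expected because protocol 6.2.3 sets a trigger criterion at estradiol of 5,000 pg/mL or more. The documents do not support that step. The criterion is marked "18,355 pmol/L) (local laboratory", whereas the endpoint is measured centrally, and a local clinical threshold does not locate the central assay's ULOQ. Protocol 4.1.2 also excludes women with polycystic ovarian syndrome or a previous OHSS episode or exuberant response. The central laboratory's procedures are not among the documents, so silence on dilution does not show that none is done. All of this stands.

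A reader might also infer that the rule builds in a bias toward the similarity the trial hopes to show. That goes too far. The direction depends on the two log SDs, and no similarity test or margin exists for the hormones. The extrapolation under test in protocol 3.5.4 concerns oocytes. Estradiol enters through the definition in protocol 1.2; nothing comparable is said of progesterone.

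Nor is a too-narrow interval a substantial separate defect: at 20% the model SE is 0.0612 against a true 0.0629. The p-value hardly moves either: with log SD 0.7 and a true ratio of 1.20, the test statistic goes from 2.13 to 2.03 at 20%.

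What survives is that the plan fixes a rule whose bias grows with the share above the ULOQ, and does not provide for reporting that share.

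**Conclusion.** The point holds conditionally and is minor. If a material share of estradiol values exceeds the central ULOQ, substitution attenuates the log ratio by about that share when log SDs are similar. With a log SD of 0.6 and a true ratio of 1.20, that means an estimate of 1.16 at 20% above the limit and 1.14 at 30%. At 5% the shift is 0.008 on the log scale (0.1823 − 0.1743), small beside an uncensored half-width of 1.968 × 0.6 × √0.015 = 0.145. At 2% or less it can be ignored.

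The actual size cannot be determined from the documents. The figures rest on log-normality, on the assumed SD and ratio, and, for coverage, on a two-group comparison instead of the full ANCOVA. Because the endpoints are secondary and the analyses descriptive, no formal error rate is affected.

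**What to change.** In SAP 10.2:

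- Report the number of values above the ULOQ by arm, and state the ULOQ.
- If there are any such values, fit the same log-scale model (treatment, AMH level, log day-1 value) by maximum likelihood with them treated as right-censored, at least as a pre-specified sensitivity analysis.
- Keep the LLOQ/2 rule for the day-1 covariate and for low outcome values. Censoring the outcome does not deal with a covariate below the LLOQ, and nothing here argues for changing the lower-end rule.

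The cost is one or two SAP sentences and a standard censored-regression routine; no new data are needed. With no value above the ULOQ, the planned ANCOVA stands unchanged. The small downside is reliance on log-normality in the upper tail, where the data cannot check it.
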